15.4 Vital Signs

The following Vital Signs measurements will be reported for this study:

- Systolic Blood Pressure (mmHg)
- Diastolic Blood Pressure (mmHg)
- Pulse rate (bpm)
- Respiratory Rate (breaths/ min)
- Temperature (°C)
- SpO₂(%)
- Weight (kg)
- Height (cm)
- BMI (kg/ m²)

The following summaries will be provided for vital signs data:

- Actual and change from baseline by visit
- Incidence of abnormal values
- · Listing of Patients meeting abnormal criteria

15.4.1 Vital Signs Abnormal Criteria

Markedly abnormal quantitative Vital Signs measurements will be identified in accordance with the following predefined abnormal criteria:

Table 3. Abnormal criteria for vital signs assessments

Vital sign	Value	Patient age at visit	
		< 18 years	≥ 18 years

Document: Document path and title

Template No.: RWI_TP_BIOS0013 Revision 2 Reference: RWI_WI_BIOS0015

Systolic blood pressure (mmHg)	High		≥ 95 th percentile of the age and height group ¹	≥ 180 with increase from updated baseline ⁵ or ≥ 20 mmHg
	Low		≤ 5 th percentile of the age and height group ¹	≤ 90 with decrease from updated baseline ⁵ or ≥ 20 mmHg
Diastolic blood pressure (mmHg)	High		≥ 95 th percentile of the age and height group ¹	≥ 105 with increase from updated baseline ⁵ or ≥ 15 mmHg
	Low		≤ 5 th percentile of the age and height group ¹	≤ 50 with decrease from updated baseline ⁵ or ≥ 15 mmHg
Oral body	High		≥ 38.4	≥ 39.1
temperature (°C)	Low		≤ 35.0	≤ 35.0
Pulse rate (bpm) ²	High	12-18 months	> 140	≥ 120 with increase from updated baseline ⁵ or ≥ 15 mmHg
		18-24 hours	> 135	
		2-3 years	> 128	
		3-4 years	> 123	
		4-6 years	> 117	
		6-8 years	> 111	
		8-12 years	> 103	
		12-15 years	> 96	
		≥ 15 years	> 92	
	Low	12-18 months	< 103	≤ 50 with decrease from updated baseline ⁵ or ≥ 15 mmHg
		18-24 hours	< 98	
		2-3 years	< 92	
		3-4 years	< 86	
		4-6 years	< 81	
		6-8 years	< 74	
		8-12 years	< 67	
		12-15 years	< 62	
		≥ 15 years	< 58	

Document: Document path and title

Template No.: RWI_TP_BIOS0013 Revision 2 Reference: RWI_WI_BIOS0015

Weight	High		Increase from baseline³ of ≥ 2 BMI-for-age percentile cetagories⁴	Weight increase from updated baseline ⁵ of ≥ 10%
	Low		Decrease from baseline³ of ≥ 2 BMI-for-age percentile cetagories⁴	Weight decrease from updated baseline ⁵ of ≥ 10%
Respiratory rate	High	12-18 months	> 46	≥ 30
(breath per minutes) ²		18-24 hours	> 40	
minutes)-		2-3 years	> 34	
		3-4 years	> 29	
		4-6 years	> 27	
		6-8 years	> 24	
		8-12 years	> 22	
		12-15 years	> 21	
		≥ 15 years	> 20	
	Low	12-18 months	< 28	≤ 10
		18-24 hours	< 25	
		2-3 years	< 22	
		3-4 years	< 21	
		4-6 years	< 20	
		6-8 years	< 18	
		8-12 years	< 16	
		12-15 years	< 15	
		≥ 15 years	< 13	

¹ Blood pressure percentiles were calculated for each blood BP record using the method described in Appendix B of National High Blood Pressure Education Program Working Group on High Blood Pressure in Children and Adolescents 2004

Document: Document path and title

Template No.: RWI_TP_BIOS0013 Revision 2 Reference: RWI_WI_BIOS0015

Effective Date: 15Oct2021

.

² Fleming et al 2011

³ Baseline BMI-for-age weight status categories are underweight (less than the 5th percentile), healthy weight (5th percentile to less than the 85th percentile), overweight (85th to less than the 95th percentile) and obese (equal to our greater than 95th percentile).

⁴ BMI-for-age percentiles categories (P3, P5, P10, P25, P50, P75, P85, P90, P95, P99 are obtained from the WHO Growth Charts (http://www.who.int/childgrowth/en/); For patients less than 2 years old, growth charts are based on recumbent length instead of height, which is not collected in the study. As an approximation, height collected in the study is considered as equal to the

Page 30 of 45

recumbent length

⁵ Updated baseline was the last value collected before the 18th birthday.

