5.2 Exclusion criteria

Participants meeting any of the following criteria are not eligible for inclusion in this study.

- 1. Previous OAV101 use or previous use of any AAV9 gene therapy
- 2. BMI < 3rd percentile based on WHO Child Growth Standard
- 3. Participant with history of aspiration pneumonia or signs of aspiration (eg, coughing or sputtering of food) within 4 weeks prior to screening
- 4. Participant dependent on gastrostomy feed tube for 100% of nutritional intake
- 5. Anti-AAV9 antibody titer > 1:50 as determined by ligand binding immunoassay at the time of screening
- 6. History of gene therapy, hematopoietic transplantation, or solid organ transplantation
- 7. Inability to take corticosteroids
- 8. Concomitant use of immunosuppressive therapy, plasmapheresis, immunomodulators such as adalimumab, or immunosuppressive therapy within 3 months prior to gene replacement therapy (eg, cyclosporine, tacrolimus, methotrexate, rituximab cyclophosphamide, IV immunoglobulin)
- 9 Requiring invasive ventilation, tracheostomy or awake non-invasive ventilation (standard of care nocturnal BiPAP is not considered exclusionary)
- 10. Administration of vaccines 2 weeks prior to infusion of OAV101
- 11. Awake hypoxemia (O₂ saturation <95%) or awake oxygen saturation level decrease between screening and dosing that is clinically significant, as per investigator judgment.
- 12. Clinically significant neurologic or neuromuscular conditions other than SMA as determined by the principal Investigator
- 13. Clinically significant abnormalities in laboratory test results at Screening as determined by the Investigator
- 14. Hepatic dysfunction (i.e. AST, ALT, bilirubin, GGT or GLDH, \geq ULN; CTCAE \geq 1) at Screening (with the exception of isolated AST elevation: in the absence of other liver laboratory abnormalities, isolated AST elevation is not considered exclusionary)
- 15. Excluding SMA, any medically unstable condition considered clinically significant by the Investigator, including cardiomyopathy, hepatic dysfunction, kidney disorder, endocrine disorder, GI disorders, metabolic disorders, severe respiratory compromise and significant brain abnormalities at either Screening or Baseline that, in the opinion of the investigator, would interfere with the overall interpretation of safety or efficacy of the study
- 16. Presence of a confirmed or suspected active infectious process from screening and up to dose administration

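### SAP Table 3 cannot flag weight loss in a child whose baseline BMI lies between the 3rd and 5th percentiles, counts uneven bands elsewhere, and has no SpO2 criterion

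*SAP*

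**What the plan says.** SAP 15.4 lists weight, height, BMI and SpO2 among the vital signs to be reported. It plans three displays: actual values with change from baseline by visit, an incidence table of abnormal values, and a listing of patients who meet abnormal criteria. SAP 15.4.1 makes Table 3 the means of identifying markedly abnormal measurements.

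For patients under 18, the Low weight row of Table 3 reads "Decrease from baseline³ of ≥ 2 BMI-for-age percentile cetagories⁴" and the High row reads "Increase from baseline³ of ≥ 2 BMI-for-age percentile cetagories⁴". Superscript 4, on the word for categories, leads to a list of cut points: "BMI-for-age percentiles categories (P3, P5, P10, P25, P50, P75, P85, P90, P95, P99 are obtained from the WHO Growth Charts". Superscript 3, on the word baseline, leads to a different, four-group scale: "Baseline BMI-for-age weight status categories are underweight (less than the 5th percentile), healthy weight", followed by overweight and obese groups cut at P85 and P95.

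Protocol 5.2 excludes "BMI < 3rd percentile based on WHO Child Growth Standard". The same section has an exclusion that begins "Awake hypoxemia (O₂ saturation <95" per cent. Protocol 8.4.3 names oxygen saturation as a collected vital sign.

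Table 3 has rows for systolic and diastolic pressure, temperature, pulse, weight and respiratory rate, and none for SpO2. Protocol 16.1.1 carries the same table and also has no SpO2 row.

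**The concern.** A flag based on a count of categories can fire only if there are enough categories left to cross. The BMI entry limit sits at the lowest cut point of the scale, so the thinnest eligible children start one step from the bottom of a rule that needs two steps. For them the Low flag is structurally unreachable. It also matters that the categories differ in width: the same change in BMI z-score may or may not be flagged, depending only on where the child started.

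The SpO2 gap is simpler. The SAP lists SpO2 and plans an abnormal-value table and listing, but gives no criterion by which an SpO2 value could count as abnormal.

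At stake is whether the abnormal-value table and listing can be read at face value. A zero for low weight could mean that no child lost weight, or that the child who did was one the rule cannot flag. An SpO2 line would be zero or absent by construction.

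**Working it through.** **Inputs.** Cut points P3, P5, P10, P25, P50, P75, P85, P90, P95, P99 (SAP Table 3, footnote 4); flag at a move of two or more categories (Table 3); entry limit P3 (Protocol 5.2); approximately 15 participants (Protocol 12.7.1). I take below P3 and P99 or above as categories too, giving 11 bands. If below P3 were not a category, the floor would be worse. The documents give no figure of their own to reproduce here.

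**Step 1: convert to SD.** Assuming BMI-for-age percentiles map to standard normal z-scores, the cut points are -1.881, -1.645, -1.282, -0.674, 0, 0.674, 1.036, 1.282, 1.645 and 2.326.

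**Step 2: limits of the rule.** A two-category move must cross the whole adjacent band. So the smallest flagged move equals the width of the adjacent band, and the largest unflagged move approaches the width of the child's own band plus the adjacent one. In SD:

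| Baseline band | Smallest fall flagged | Largest fall missed | Smallest rise flagged | Largest rise missed |
|---|---|---|---|---|
| P3 to <P5 | never | no limit | 0.363 | 0.599 |
| P5 to <P10 | 0.236 | 0.599 | 0.607 | 0.970 |
| P10 to <P25 | 0.363 | 0.970 | 0.674 | 1.282 |
| P25 to <P50 | 0.607 | 1.282 | 0.674 | 1.349 |
| P50 to <P75 | 0.674 | 1.349 | 0.362 | 1.036 |
| P75 to <P85 | 0.674 | 1.036 | 0.245 | 0.607 |
| P85 to <P90 | 0.362 | 0.607 | 0.363 | 0.608 |
| P90 to <P95 | 0.245 | 0.608 | 0.681 | 1.045 |
| P95 to <P99 | 0.363 | 1.045 | never | no limit |
| P99 or above | 0.681 | no limit | never | no limit |

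- Floor: from just above P5, a fall of -1.645 - (-1.881) = 0.236 SD is flagged. From just below P5, no fall is.
- Mid-range: from just under P75 down to P25 is 0.674 + 0.674 = 1.35 SD (unrounded 1.349), not flagged. The same distance upward, from P25 to just under P75, is also missed.
- Upper range: a rise from just under P85 to P90 is 1.282 - 1.036, about 0.245 SD, and is flagged. So is a fall of 0.245 SD from P90 to just under P85.

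The list in Protocol 16.1.1 ends in P91 where the SAP has P99. Taken literally and sorted, that adds a band of 0.059 SD (P90 to P91). It changes neither the floor nor the 1.35 SD figure.

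**Step 3: how many children sit on the floor.** For mean z-score m and SD 1 (assumptions), the share of eligible children in P3 to <P5 is [Φ(-1.645 - m) - Φ(-1.881 - m)] / [1 - Φ(-1.881 - m)].

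- m = 0: 0.02 / 0.97 = 2.06%; times 15 = 0.31 children.
- m = -0.5: 4.63%; times 15 = 0.70.
- m = -1: 8.67%; times 15 = 1.30.

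**Step 4: SpO2.** Setting the SAP 15.4 list beside the Table 3 rows, SpO2 is in the first and not in the second. No SpO2 value from any child can meet a criterion.

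**The case against.** The strongest reply is that little depends on these flags. The primary vital-sign endpoint is change from baseline, and SAP 15.4 still tabulates weight, BMI and SpO2 by visit; SAP 15.1.1 adds minimum and maximum. Findings judged clinically significant can be reported as adverse events (Protocol 10.1.1), and SAP 7.3 brings clinically significant abnormal values into the safety assessment. Nothing is tested, and few children are likely to sit on the floor. Table 3 also follows the protocol appendix.

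Most of this stands, and it limits the point to the abnormal-value table and listing. It does not remove it. By-visit means can hide one child's decline, and a minimum neither identifies the child nor counts how many were abnormal. Under SAP 7.3, unscheduled values are kept out of the by-visit summaries, so an unscheduled desaturation would be picked up only through a judgement of clinical significance, not a predefined criterion.

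Some stronger readings are tempting and should be resisted:

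- That weight loss or desaturation disappears from the outputs, or that SpO2 is the only respiratory sign. The by-visit tables remain, and respiratory rate is measured and has its own Table 3 rows.
- That the rule is tilted against detecting loss. Apart from the floor, the unevenness runs both ways, and a child at P95 or above can never be flagged for a rise.
- That sensitivity differs fivefold, from 1.34 SD missed (P74.9 to P25.1) against 0.26 SD flagged (P84.9 to P90.1). That sets a nearly largest missed move against a nearly smallest flagged one. Like for like, the ratios are 0.674/0.245 = 2.8 for the smallest flagged moves and 1.349/0.607 = 2.2 for the largest missed.
- That the four groups of footnote 3 are the counting scale, so that no child below P85 could be flagged low. The superscripts attach footnote 4 to the categories and footnote 3 to baseline. The SAP should say so outright, but the text does not impose the other reading.

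**Conclusion.** The point holds within a narrow scope. As written, Table 3 cannot flag weight loss of any size from a baseline in P3 to <P5. Its thresholds elsewhere vary from about 0.24 to 0.68 SD for the smallest flagged move, with moves of up to 1.35 SD unflagged mid-range. It also cannot flag any SpO2 value.

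The floor and the SpO2 gap follow from the text alone. The SD figures assume normal z-scores. The expected number of children on the floor, about 0.3 to 1.3 of 15, rests on assumed mean z-scores from 0 to -1 with SD 1; the documents give no BMI distribution for this population.

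Only the abnormal-value incidence table and listing are affected. The primary adverse-event analysis and the change-from-baseline summaries are not. The correction is worth making because it is cheap and the rule gives a wrong result where stated.

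**What to change.** In SAP Table 3:

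1. Keep the two-category rule and add to the Low weight row: or any post-dose BMI-for-age newly below P3 (baseline at or above P3).
2. State that footnote 4 is the scale on which categories are counted.
3. Add an SpO2 row that flags values below 95%, the figure in the protocol's entry criterion, and notes awake or asleep state where recorded. This is an analysis flag only and implies nothing about clinical management.
4. Declare the departure from Protocol 16.1.1 in SAP 4.3, which at present reports no changes.

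The cost is SAP wording and programming. Weight, height, age and SpO2 are already collected.

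There are downsides. A child hovering at P3 may be flagged after a very small change: P3.1 to P2.9 is about 0.03 SD. The documents do not say that awake or asleep state is recorded with SpO2, so some flagged values may be from sleep. The SAP table will no longer match the protocol appendix.

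This leaves the mid-range unevenness in place. Replacing the band count with a 1 SD z-score rule would even it out, but would drop falls that are flagged now, such as P50.1 to P24.9 (0.68 SD) and P10.1 to P4.9 (0.38 SD). The 1 SD threshold also has no source in the documents, so I do not recommend that replacement here.

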15.5 Other Safety Assessments

Not applicable

16. SECONDARY OUTCOMES

All secondary outcomes will be analyzed for FAS.

16.1 Effectiveness outcome

The number and proportion of participants achieving each WHO developmental milestone will be presented at 6-, 12-, and 18- months post-infusion.

The analysis will take into account the following intercurrent events using a composite strategy:

- Intake of prohibited concomitant medications (as described in protocol section 6.6.2 Prohibit medications)
- Discontinuation from study due to reasons other than death

This means that if the any of the intercurrent events of interest occur the participant will be regarded as a non-responder from when the first intercurrent event of interest occurs.

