6.2.1 Concomitant therapy

The Investigator should instruct the participant and his/her parents/caregivers to notify the study site about any new medications he/she takes after the participant was enrolled into the study.

All medications, procedures, and significant non-drug therapies (including physical therapy and blood transfusions) that are ongoing or administered after the participant was enrolled into the study must be recorded on the appropriate CRFs.

Each concomitant drug must be individually assessed against all exclusion criteria/prohibited medication (Section 5.2 and Section 6.2.2). If in doubt, the Investigator should contact the Novartis medical monitor before enrollment of a participant or allowing a new medication to be started. If the participant is already enrolled, contact Novartis to determine if the participant should continue participation in the study.

Participants are encouraged to follow all routinely scheduled immunizations, recommended by local health authorities and consistent with Section 6.2.2, throughout the study. Vaccinations that include palivizumab prophylaxis (also known as Synagis) to prevent RSV infections are also recommended in accordance with the guidance of local health authorities.

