6.2.2 Prohibited medication

Except for concomitant medication allowed per protocol (see Section 6.2.1), prednisolone, and/or any non-excluded medications which may be required to treat AEs, no medication other than study treatment will be allowed from the date the informed consent/assent is signed until all of the study completion evaluations have been performed.

Concomitant use of any of the following medications are prohibited:

- Concomitant medication with the intent to treat SMA
- Any investigational medication other than OAV101
- Use of intravenous immunoglobulins and non-live vaccines 4 weeks after infusion of OAV101; unless required for treatment of adverse events.
- Live vaccines are prohibited while receiving corticosteroids
- The use of immunosuppressive therapies, including but not limited to, for example, cyclosporine, tacrolimus, methotrexate, cyclophosphamide, IVIG, rituximab, and adalimumab; unless required for treatment of adverse events

Given the nature and profile of the treatment, i.e., gene therapy, there are no PK/PD drug interactions expected.

The Investigator should instruct the participant/caregiver to notify the study site about any new treatments, including herbal and over the counter medications the participant takes after the start of study treatment. All prohibited medications and significant non-drug therapies administered after the participant starts study treatment must be recorded in the eCRF.

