12.4.2 Statistical model, hypothesis, and method of analysis

No statistical hypothesis testing will be performed.

Treatment-emergent AEs are defined as any event that begins or worsens in severity after infusion of OAV101 through to the last study visit. The incidence of TEAEs will be summarized according to MedDRA as follows: overall by SOC and PT, overall, by SOC, PT and severity, suspected treatment-related AEs by SOC and PT, SAEs by SOC and PT.

Adverse events of special interest (AESI) are defined by the important identified risk and important potential risk as presented in the effective Risk Management Plan (RMP). MedDRA search criteria to retrieve AEs indicative of these risks are updated on a regular basis at the

OAV101 program level. The incidence of treatment emergent AESIs will be summarized. Descriptive summary statistics for the change from baseline in cardiac safety assessments, clinical laboratory measurements, and vital signs will be summarized descriptively by visit/timepoint. Mean, standard deviation, median, minimum, and maximum will be presented. For each applicable visit/timepoint, only participants with a baseline and a measurement for that timepoint will be included in the summary. Categorical cardiac safety assessments, clinical laboratory measurements, and vital signs data will be presented as frequencies and percentages.

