4. STUDY DESIGN

4.1 General Description

This is an open-label, single arm, multi-center study to evaluate the safety, tolerability, and efficacy of IV OAV101 in symptomatic SMA pediatric participants. The study will enroll participants that weigh \leq 17 kg.

Participants who meet eligibility criteria at Screening and Baseline visits will receive a single dose of IV OAV101 on Day 1 (Treatment period) at the approved dose of 1.1e14 vg/kg and will be followed for a period of 18 months. The study will include a 20-day screening period in which there will be 2 Screening visits, during which, eligibility will be assessed (Screening 1), weight will be collected for dose calculation (Screening 2), and baseline assessments will be performed prior to treatment. For the study duration, participants will be completing visits as defined in the Schedule of Assessments. On Day -1, participants will be admitted to the hospital for pretreatment baseline procedures including prednisolone treatment per study protocol. On Day 1, participants will receive a single IV infusion of OAV101. Participants may be discharged 12-48 hours after the infusion, based on Investigator judgment.

Safety monitoring will be performed on an ongoing basis per protocol requirement and will be evaluated by the clinical safety team as well as DMC. An interim analysis for safety and efficacy will be performed once the last participant completes 6-months of follow-up and will include all available data up until that data cut-off. Final analysis will be planned once all participants have completed Month 18 End of Study (EOS) assessments.

After study completion eligible participants will be invited to enroll into RESTORE registry study to collect additional safety and efficacy data.

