13. MEDICATIONS

Medications will be presented for the FAS and coded using WHO drug dated March-2022 or later.

The Anatomical Therapeutic Chemical (ATC) class coding will follow level 3 structure.

See Appendix 2 for handling of partial dates for medications.

'Concomitant' medications are medications which:

- Started prior to, on or after the study medication dosing and started no later than
 30 days following end of study,
- AND ended on or after the date study medication dosing or were ongoing at the end of the study.

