Appendix table 2. Algorithm for Prior and Concomitant Medications:

START DATE	STOP DATE	ACTION
Known	Known	If stop date < study med start date, assign as prior
		If stop date >= study med start date and start date <= end of treatment, assign as concomitant
		If stop date >= study med start date and start date > end of treatment, assign as post study
	Partial	Impute stop date as latest possible date (i.e. last day of month if day unknown or 31st December if day and month are unknown), then:
		If stop date < study med start date, assign as prior
		If stop date >= study med start date and start date <= end of treatment, assign as concomitant
		If stop date >= study med start date and start date > end of treatment, assign as post treatment
	Missing	If stop date is missing could never be assumed a prior medication
		If start date <= end of treatment, assign as concomitant
		If start date > end of treatment, assign as post treatment

Document: Document path and title

Template No.: RWI_TP_BIOS0013 Revision 2 Reference: RWI_WI_BIOS0015

Page 43 of 45

START	STOP	ACTION
DATE	DATE	
Partial	Known	Impute start date as earliest possible date (i.e. first day of month if day unknown or 1 st January if day and month are unknown), then:
		If stop date < study med start date, assign as prior
		If stop date >= study med start date and start date <= end of treatment, assign as concomitant
		If stop date >= study med start date and start date > end of treatment, assign as post treatment
	Partial	Impute start date as earliest possible date (i.e. first day of month if day unknown or 1 st January if day and month are unknown) and impute stop date as latest possible date (i.e. last day of month if day unknown or 31 st December if day and month are unknown), then:
		If stop date < study med start date, assign as prior
		If stop date >= study med start date and start date <= end of treatment, assign as concomitant
		If stop date >= study med start date and start date > end of treatment, assign as post treatment
	Missing	Impute start date as earliest possible date (i.e. first day of month if day unknown or 1 st January if day and month are unknown), then:
		If stop date is missing could never be assumed a prior medication
		If start date <= end of treatment, assign as concomitant
		If start date > end of treatment, assign as post treatment

Document: Document path and title

Template No.: RWI_TP_BIOS0013 Revision 2 Reference: RWI_WI_BIOS0015

Page 44 of 45

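### The milestone rule counts any prohibited medication as failure, so one routine vaccine in the prohibited window overrides an observed milestone; limit the trigger to SMA-directed and other investigational drugs

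*SAP*

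**What the plan says.** The secondary endpoint is the proportion of participants achieving each WHO motor milestone at 6, 12 and 18 months. Protocol 12.4.7 and SAP 16.1 handle two intercurrent events by a composite strategy: discontinuation for reasons other than death, and prohibited medication. The SAP words the second as "Intake of prohibited concomitant medications (as described in protocol section 6.6.2 Prohibit medications". From the first such event the child counts as a non-responder. Neither document limits this by drug class or duration, and neither lets the child return to responder status.

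The prohibited list is in protocol 6.2.2. It names drugs given to treat SMA, other investigational drugs, immunoglobulins and non-live vaccines for 4 weeks after infusion, and immunosuppressants. It also says: "Live vaccines are prohibited while receiving corticosteroids". Immunoglobulins, non-live vaccines and immunosuppressants are exempt when needed to treat an adverse event. The same section says that "there are no PK/PD drug interactions expected". Protocol 6.2.1 says "Participants are encouraged to follow all routinely scheduled immunizations", provided this is consistent with 6.2.2.

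SAP 13 defines a concomitant medication as one that "Started prior to, on or after the study medication dosing and started no later than" 30 days after the end of the study, and that ended on or after dosing or was still ongoing. Appendix table 2 applies a different limit: "If stop date >= study med start date and start date <= end of treatment, assign as concomitant". The SAP does not define end of treatment.

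**The concern.** A composite strategy suits an event that means the treatment failed, or that makes later success impossible to credit to it. Starting another SMA drug is such an event. A vaccine given in the wrong week is not obviously one, and the documents state no link between a vaccine and motor function. Yet the rule gives both the same permanent consequence. In a single-arm study of about 15 children, a few such cases would visibly lower the reported proportions for a reason unrelated to milestones.

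The wrong section number adds to this. A programmer who follows it reaches a section on treating adverse events that contains no prohibited list. The undefined cut-off in Appendix table 2 raises a further question: whether a drug started well after infusion would be flagged as concomitant at all.

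**Working it through.** **The plan's own figure.** Protocol 12.7.1 gives about a 90% chance of seeing at least one adverse event of true incidence 14% in 15 participants: 1 − 0.86^15 = 0.896, which reproduces. It does not concern milestones, and the documents give no target or expected rate for them.

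**Inputs from the documents.** N is approximately 15 (protocol 12.7.1). Milestones are summarised at weeks 26, 52 and 78, nominally Days 183, 365 and 547 (SAP Table 1 and 16.1.1). The prohibited window for non-live vaccines is 4 weeks. Prednisolone runs at least 30 days at 1 mg/kg/day, then falls by 0.25 mg/kg per week (protocol Table 6-2).

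**Step 1: apply the rule.** A routine non-live vaccine on Day 20 falls within 28 days of infusion and is not treatment of an adverse event. It is therefore prohibited. The child becomes a non-responder on Day 20, before every post-infusion milestone analysis visit, and stays one at all three.

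**Step 2: length of the windows.** Non-live vaccines: 28 days. Live vaccines, with the shortest steroid course: 30 + 3 × 7 = 51 days to 30 + 4 × 7 = 58 days, depending on whether three or four weekly steps are counted. This is a minimum, because the full steroid dose continues until liver tests return to baseline.

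**Step 3: size.** With all 15 children in the denominator, each child who met the milestone but is failed only for a vaccine costs 1/15 = 6.7 points; two cost 2/15 = 13.3 and three cost 3/15 = 20.0. As an illustration, assume 8 of 15 are observed walking. Then 8/15 = 53.3% is reported as 7/15 = 46.7%, 6/15 = 40.0% or 5/15 = 33.3% with one, two or three such children.

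**Step 4: how likely is one case?** The documents give no rate, so a range of assumed per-child probabilities q is used. The chance of at least one mistimed vaccine among 15 is 1 − (1 − q)^15:

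| Assumed q | At least one in 15 |
|---|---|
| 2% | 26% |
| 5% | 54% |
| 10% | 79% |
| 20% | 96% |

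A vaccine changes a proportion only if that child also met the milestone.

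**Step 5: the date algorithm.** Three readings of end of treatment can be drawn from the SAP. The first is the infusion day, since SAP 4.1 describes a "single dose of IV OAV101 on Day 1 (Treatment period". The second is the last steroid dose, because SAP 14 calls the corticosteroid a secondary study medication; Day 30 or about Day 58 is assumed here. The third is the last visit, where the on-treatment period in SAP 7 ends.

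| Rule | SMA drug from Day 240, ongoing | Vaccine on Day 20 |
|---|---|---|
| Appendix table 2, Day 1 | not concomitant | not concomitant |
| Appendix table 2, last steroid dose | not concomitant | concomitant |
| Appendix table 2, last visit (Day 547) | concomitant | concomitant |
| SAP 13 | concomitant | concomitant |

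An SMA drug started before infusion and still ongoing, or ongoing with a missing start date, is concomitant under every reading.

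**The case against.** A reader might infer that the rule fails children for vaccines and at the same time lets an SMA drug begun in, say, month 8 escape, so that the endpoint is biased in both directions. The documents do not support that. SAP 16.1 defines the trigger by the protocol's prohibited-medication section, not by the Appendix table 2 flag. Protocol 6.2.2 applies its prohibition from consent until the study completion evaluations are done. SAP 13 would count such a drug as concomitant, and refers to Appendix 2 only for partial dates. Even if the flag did drive the trigger, the two errors coincide only when end of treatment means the last steroid dose. On the Day 1 reading the vaccine drops out as well, and on the last-visit reading the SMA drug is caught. The remaining gap between the last visit and 30 days after the end of the study cannot affect a milestone already assessed by week 78.

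The plan also makes mistimed vaccines less likely. Encouragement to immunise is subject to 6.2.2, vaccination must be up to date at entry, and protocol 6.2 withholds vaccines around infusion. The section on drug interactions concerns PK/PD and is not a statement about motor function. Counting every prohibited drug as failure is prespecified, conservative and identical in both documents, and the analysis is descriptive: "No statistical hypothesis testing will be performed". The vaccine argument does not by itself settle how immunosuppressants and immunoglobulins should count.

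These points limit the likely frequency and rule out any claim about error rates. They do not change what the rule does when a mistimed vaccine occurs. Conservatism is also no reason to report only this version: the available text specifies no milestone table free of the composite rule, and the SAP plans no sensitivity analysis.

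**Conclusion.** The point holds for the breadth of the trigger and for the wrong cross-reference. Reading 6.6.2 as 6.2.2, which is the only section with a prohibited list, a routine vaccine in the prohibited window turns observed milestones into failures at weeks 26, 52 and 78. The cost is 6.7 points per affected child, assuming 15 children in the denominator. The number of such children, the rates in Step 4 and the 8 walkers are assumptions.

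The conflict between SAP 13 and Appendix table 2 is real but conditional. It leaves a later-started SMA drug unflagged only if the trigger is programmed from that flag and end of treatment is read as Day 1 or the last steroid dose. The SAP says neither.

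It would also be too strong to call this the study's only efficacy endpoint, since parts of the SAP are not visible. It is the only secondary efficacy endpoint that can be seen. The effect is on reported proportions, not on any test.

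**What to change.** All changes are to the analysis text; no vaccine or medication rule changes.

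- SAP 16.1: correct the reference to protocol 6.2.2.
- Protocol 12.4.7 and SAP 16.1: limit the medication trigger for non-response to drugs given to treat SMA and other investigational drugs, the first two items in 6.2.2.
- For the other prohibited items, analyse the milestone as observed and list each intake as a protocol deviation.
- Add a supplementary milestone table that applies the all-prohibited rule, so that both versions can be compared.
- Appendix table 2: replace end of treatment with the SAP 13 limit throughout.

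The cost is wording in two documents and one extra table. The downside is that the main summary becomes less strict for immunosuppressants, immunoglobulins and vaccines; the supplementary table shows how much this matters.
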